Clinical conditions during bonding procedure include a risk of contamination of the etched surface by saliva. Saliva contamination of the enamel surface is regarded as the most common reason for bond failure (**Zachrisson, 1977; Paschos et al.,**

2008). Acid-etched enamel absorbs saliva, which reduces the surface energy and renders the surface less favorable for bonding (**Evancusky and Meiers, 2000; Kumar et al., 2012**). When the etched enamel is wet, most of the porosities become plugged, and the penetration of the resin is impaired, which results in resin tags of insufficient number and length (**Hormati et al., 1980; Silverstone et al., 1985; Öztoprak et al., 2007**).

It must be noted, however, that the use of the terms ‘moist’ or ‘wet’ implies the presence of water, whilst saliva or crevicular fluid are considered ‘contaminants’. Although the presence of water can be prevented by adopting moisture control precautions during bonding procedures, the orthodontist is often faced with the problem of bonding in an environment with increased contamination risk from saliva (**Cacciafesta et al., 1998; Wendl and Droschl, 2004**). Because of their hydrophobic properties and absence of chemical adhesion, conventional bisphenol A-glycidyl methacrylate (Bis-GMA) adhesives require dry etched enamel for mechanical adhesion (**Hormati et al., 1980; Grandhi et al., 2001**).

The failure rate of bonding to molars was greater than that of bonding to anterior teeth (**Jung, 2014; Roelofs et al., 2016**). A possible solution to this problem was offered by the development of the moisture insensitive primers (MIP). These novel bonding materials contain hydrophilic components such as Hydroxyethyl Methacrylate (HEMA), which act as a wetting agent, allowing a lower contact angle and rapid extension of the molecule which bonds easily to the resin composite. In addition, they contain alcohol, which acts as a drying agent that seeks out moisture, evaporates it from the bonding field, and brings the resin in; thus, ensuring an efficient bonding (**Webster et al., 2001; Gange, 2015; Hadrous et al., 2019**).

These primers are commercially available nowadays as Transbond MIP (3M Unitek Dental Products, Monrovia, CA, USA) and Assure Plus universal bond (Reliance, Itasca, IL, USA). In the cloud, many in vitro studies supports the manufacturers' claim that these two novel orthodontic systems provides sufficient shear bond strength of orthodontic attachments bonded under moisture contaminated conditions (**Goswami et al., 2014; Kumar et al., 2018; Hadrous et al., 2019; Stefański et al., 2019**).

Although these in vitro measurements provide useful information about the bonding efficiency of different types of materials, they should be interpreted with caution because of inherent limitations and because they cannot take into account a number of factors that play an important role in the mouth (**Eliades and Brantley, 2000**). For your information, no previous clinical study was conducted to evaluate the efficacy of these primers on bond failure rate, therefore; this randomized clinical trial will be conducted to be more representative of the clinical reality.

Aim and Objectives

Aim

To evaluate the clinical effectiveness of moisture insensitive primers in bonding molar tubes under moisture contaminated conditions.

Objectives

- 1- To evaluate and compare the clinical bond failure and survival rate of molar tubes using two moisture insensitive primers under moisture contaminated condition.

2- To compare the effectiveness of these primers between different arches, sides, gender and age differences.

The null hypothesis is that “there is no significant differences in the bond failure rate of molar tubes using Transbond MIP and Assure Plus universal bond under moisture contamination during the function of archwires used during leveling and alignment stage of orthodontic treatment”.

Methodology

Study design

A single-operator, a split-mouth, cross-quadrant, randomized controlled trial (RCT), with 1:1 allocation ratio.

Settings

Orthodontic patients seeking for orthodontic treatment with fixed orthodontic appliance will be recruited for this study. The study will be conducted in the Orthodontic Clinic at the College of Dentistry/University of Baghdad in addition to private dental clinics and Bab Al-Muadham specialized dental center in Baghdad, Iraq. Clinicians will be either specialist orthodontists or under training to become specialist orthodontists.

Ethical approval will be obtained from the Ethics Committee of College of Dentistry/University of Baghdad prior to study commencement. The patients were first evaluated by the principal investigator ([name]) to see if they were eligible for the research. Those who meet the inclusion criteria will be asked to assigned a comprehensive consent form prior to the start of trial.

Subjects/Materials

Subjects

Patients seeking for orthodontic treatment and their treatment will be planned with metal fixed orthodontic appliance (0.22" for both arches).

Materials

A- Orthodontic materials:

1-Moisture insensitive primers: Transbond MIP (3M Unitek Dental Products, Monrovia, CA, USA) and Assure Plus universal bonding resin (Reliance, Itasca, IL, USA).

2-Orthodontic adhesive: CONTEC lc (Dentaurum GmbH & Co. KG, [name]).

3-Molar tubes: Stainless steel Classic Roth Tube with 0.022 slot (IOS International Orthodontics Services, [name]).

4- 37% phosphoric acid: N-Etch (Ivoclar Vivadent, Schaan, Liechtenstein).

5- Metal fixed orthodontic appliance with 0.022 slot and a universal sequence of orthodontic archwires used to finish leveling and alignment stage of orthodontic treatment. Orthodontic archwires used with brackets during orthodontic treatment.

B- Other materials:

oil- and fluoride-free coarse pumice powder, a rubber prophylactic cup, distilled water, bond brush, dental cotton pellets, articulating paper (ArtEXACT, Becht, Offenburg, Germany).

Instruments/equipment

Instruments

Cheek retractors, tube tweezers, bracket position gauge, dental mirror, probe and tweezers.

Equipment

Light curing unit: (Light emitting diode, Eight teeth curing pen; Changzhou city, Jiangsu, P.R.China) Specification of light curing unit: Light intensity: 1500 mW/cm², Output wavelength: 380–515 nm.

Sample Size

To have adequate power (80%) to show a statistically significant difference ($P < 0.05$) in proportions with at least one failed molar tube after 6 months, the RCT needed 33 patients in each group using a log rank test ignoring the matching. This assumes a difference of 35 percentage points (45% versus 80%, hazard ratio = 3.6). As an approximate allowance for the effect of matching, an estimated 33 patients in total were required using a stratified log rank test for analysis (**Littlewood et al., 2001; Wenger et al., 2008**).

Procedure/Intervention

1-Sample Selection:

Thirty-three consecutive patients will be eligible for the study if they fulfill the following inclusion criteria:

1. Patients need metal fixed orthodontic appliance with 0.22";
2. Complete set of permanent dentition with fully erupted molar teeth on both arches;

3. Intact 1st molars and mainly their buccal surfaces are free from caries, fillings, or gingival hyperplasia;
4. No occlusal interferences that can affect the ideal position of molar tubes, especially in the lower arch.

2- Randomization:

The primers will be randomly allocated using a split-mouth, cross-quadrant design. In each patient, two diagonal quadrants (i.e. upper right and lower left, or vice versa) will be randomly assigned to each primer group. The split-mouth design has several advantages over a complete randomization design: it compares treatments within patients so that variation between patients is eliminated (e.g. effect of the chewing habits of the patient). Furthermore, in terms of patient recruitment, which is always difficult to accomplish in clinical trials, at most half of the patients are needed in a split-mouth design compared with the corresponding whole-mouth design (**Lesaffre et al., 2009**). A potential disadvantage of the split-mouth design is that the treatment applied to one side can have a carry-across effect on the contralateral side of the mouth. This problem is limited with randomization (**Thiyagarajah et al., 2006**).

In order to ensure an equal distribution of primers between the right and the left side of the dental arches, the mouth of each patient will be divided into quadrants and the contralateral bonding pattern will be randomly alternated from patient to patient using a random plan generator (Randomization.com). A CONSORT diagram showing the flow of patients through each stage of the trial is shown in Figure 1.

3-Blinding:

This study will be Double-blinded in which neither the patients nor the trial staff know which one of the primers a patient has received. This can be achieved by placing the two primers in two similar masked bottles and giving them numerical coding i.e. number one and number two coding for either type of primer (**Schulz and Grimes, 2002**).

[figure not shown]

Figure 1 CONSORT flow diagram showing progress of subjects through the trial.

4-Procedure:

A single operator to avoid inter-operator variation will bond all molar tubes. A standardized protocol of tooth preparation and Molar tubes bonding will be adopted for all the patients. All teeth will be isolated and cleansed with a mixture of water and pumice using a rubber-polishing cup on a low speed hand piece. The teeth will be rinsed and dried with an oil-free air syringe, and will be etched with the conventional acid etching technique (37 percent orthophosphoric acid applied for 30 seconds). They will be subsequently rinsed thoroughly with water for 10 seconds to ensure total removal of etchant according to the manufacturer's instructions.

Without drying, one coat of the patient own non-stimulated saliva will be applied to the etched and wet surface using bond brush (**Zeppieri et al., 2003; Endo et al., 2008; Goswami et al., 2014**). the excess will be blotted with a moist cotton pellet maintaining the surface moist (**Kumar et al., 2018**).

A liberal coat of the Moisture-Insensitive Primer will be applied to the etched area of the teeth destined for a specific primer (split-mouth) using a nylon bond brush. Air will be gently blown on each tooth for 2 seconds, aiming the air stream perpendicular to the enamel surface then light cured for 20 seconds.

After etching and priming, molar tubes will be bonded to the teeth with CONTEC lc adhesive according to the manufacturer's instructions. The CONTEC lc adhesive will be applied to the molar tube base. The molar tube will be positioned correctly on the buccal surface of the tooth, and pressed firmly into place to express adhesive from the rim of the molar tube base. Excess adhesive will be removed with an explorer before curing. Then, the molar tube will be light-cured with a light curing unit (1500 mW/cm², 380–515 nm.) for 20 seconds: 5 seconds each from the mesial,

distal, occlusal and gingival aspects of each tube). After curing is complete the molar tubes will be inspected for occlusal interferences using articulating paper. The sample will be excluded from the trial if any occlusal interference was observed. Initial wires will be fitted 10-15 minutes after bonding completion in the context of the straight wire technique.

All patients will receive the same instructions and will be seen at 3-4-week intervals. They will be, however, requested to inform the operator immediately and attend as soon as possible once a bond failure was apparent. They will be instructed to brush with a manual toothbrush using a fluoride-containing toothpaste.

5-Data collection:

Each patient will be monitored for 6 months. If a bond failed, the following will be recorded:

- (1) Tooth number where failure occurred;
- (2) Type of primer used;
- (3) Date of bond failure.

Only the first failure of tubes will be taken into consideration. The teeth with recycled or newer tubes replaced will not be considered.

Timetable

Table 1

	Procedure	Time (months)
1	Material preparation and availability	Two months
2	Patient recruitment	Four months
3	Follow up	Six months
4	Results analysis and interpretation	Two months
5	Thesis writing	Four months
	Total	Eighteen months

The follow up period ends after six months from the start of recruitment of each patient. A clinical trial with similar situations concluded that half (49.8 per cent) of the total bond failures occurred during the first 2 months of treatment (**Mavropoulos et al., 2003**). The probability of bond failure is greater immediately after bonding and during the first 3 months of bracket life (**Campoy et al., 2010**).

Stopping Rules:

No stopping rules.

Budget and Funding:

- The study is self-funded.

Ethical Approval:

- The protocol will be submitted to ethics committee.

Data Management and Analysis

The data will be analyzed using SPSS software version 28.0.1 (IBM, Chicago, Illinois, USA). To find if there is significant difference, the number of bonding failures will be compared using the chi-square test, the tube survival rate will be estimated using the Kaplan–Meier analysis. The Tube survival distributions with respect to primer material, tooth location (upper/lower, right/left side), patient's gender and age will be then compared by means of a log-rank test. Further analysis to investigate the effects of covariates will be carried out using the frailty Cox regression model with response time to failure.

Further Considerations

Pilot study

- A pilot study will NOT be conducted

Dissemination

- Postgraduate Thesis.

References

- Buonocore, M.G. (1955). A simple method of increasing the adhesion of acrylic filling materials to enamel surfaces. *Journal of dental research*, 34, 849-853.

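### Does leaving the excluded unit undefined at the post-bonding occlusal check undermine the comparison of the two primers?

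*Combined protocol and SAP*

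**What the plan says.** Inclusion criterion 4 (1-Sample Selection) requires: "No occlusal interferences that can affect the ideal position of molar tubes, especially in the lower arch". In 4-Procedure a second check follows once the primer has been applied and the tube cured: "After curing is complete the molar tubes will be inspected for occlusal interferences using articulating paper". The next sentence gives the consequence: "The sample will be excluded from the trial if any occlusal interference was observed". Initial wires are fitted only after that.

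On numbers, the Sample Size section concludes that "an estimated 33 patients in total were required using a stratified log rank test for analysis", and 1-Sample Selection opens with "Thirty-three consecutive patients will be eligible for the study if they fulfill the following inclusion criteria". The calculation is framed as a difference "in proportions with at least one failed molar tube after 6 months", using 45% versus 80% and a hazard ratio of 3.6.

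Data Management and Analysis compares the number of failures by chi-square and tube survival by Kaplan–Meier and log-rank. Covariate effects are then examined with "the frailty Cox regression model with response time to failure". The text defines no analysis set and gives no replacement rule. The CONSORT figure is not available to this review and may label the unit.

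**The concern.** An exclusion made after allocation and treatment always deserves a second look, and here three things are left unsaid: the unit, whether it is replaced, and how a patient left with three tubes is scored. Each seems to matter. With exactly 33 patients needed and 33 recruited, any unreplaced patient takes the trial below its planned size. The sizing outcome is at least one failure per patient and primer, so losing one tube gives one primer a single chance to fail where the other has two. A choice of rule made late could also be made with the failures in view.

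**Working it through.** **1. Reproduce the 33.** The inputs are from the Sample Size section: 80% power, P < 0.05 (two-sided assumed), 45% versus 80%. The hazard ratio fits if these are failure-free proportions: ln 0.45 / ln 0.80 = 3.578, which rounds to the stated 3.6. The failure risks are then 55% and 20%.

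Freedman events = (1.960 + 0.842)² × [(HR + 1)/(HR − 1)]² = 7.849 × (4.578/2.578)² = 24.75. Each pair (one patient per group) contributes 0.55 + 0.20 = 0.75 events, so n = 24.75/0.75 = 33.0 per group. The stated figure is reproduced.

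**2. Patient reading, no replacement.** As the plan does, treat n patients as n per group.

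- Freedman power = Φ(√(0.75n) × 2.578/4.578 − 1.96)
- Schoenfeld power = Φ(½√(0.75n) × ln 3.578 − 1.96)

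| Patients | Freedman | Schoenfeld |
|---|---|---|
| 33 | 80.0% | 88.7% |
| 32 | 78.8% | 87.8% |
| 31 | 77.5% | 86.7% |
| 28 | 73.3% | 83.2% |
| 27 | 71.7% | 81.8% |

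The documents give no exclusion rate. If 5% of patients were excluded, 33 × 0.95 = 31.4 would remain. A harsher assumption is that 5% of tubes show interference independently, with four tubes per patient (inferred from the quadrant design), and that any one of them removes the patient. Then 33 × 0.95⁴ = 26.9 remain. Keeping 33 at an assumed 5% or 10% patient exclusion means enrolling 33/0.95 = 34.7 (35) or 33/0.90 = 36.7 (37).

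An excluded patient takes tubes from both primers, so the within-patient contrast stays balanced. Only precision is affected.

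**3. Tube reading, scoring.** If tubes fail independently, at-least-one risks of 55% and 20% imply per-tube risks of 1 − √0.45 = 32.9% and 1 − √0.80 = 10.6%. A one-tube side would score 55 − 32.9 = 22.1 or 20 − 10.6 = 9.4 points lower on the at-least-one outcome. Spread over 33 patients, that is 0.7 or 0.3 points per excluded tube, and zero if the two tubes always fail together.

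That outcome appears only in the sizing. The planned analyses count tubes and follow tube survival. There an excluded tube drops out of numerator and denominator alike, and equal primers keep equal expected rates per tube. The frailty model and a patient-stratified log-rank test both accept unequal tube numbers.

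**4. Tube reading, arch mix.** Each primer has 66 tubes, 33 of them lower. If five lower tubes are lost from one primer, its lower share falls from 33/66 = 50.0% to 28/61 = 45.9%, a change of 4.1 percentage points. With an assumed upper–lower difference of 10 to 30 points, the crude rate moves by 0.041 × 10 to 0.041 × 30, or 0.4 to 1.2 points. The comparable tube-level contrast under independence is 32.9 − 10.6 = 22.3 points.

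**5. The two checks side by side.** Criterion 4 screens patients before bonding for interference that would affect tube position. The later check looks for any interference with the cured tube in place, so it cannot be made earlier. The rules overlap but do not contradict each other.

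**The case for a change.** The strongest case for acting is that the two readings could produce noticeably different trials. At the assumed 5% per tube, tube exclusion keeps 132 × 0.95 = 125.4 of 132 tubes, while patient exclusion keeps about 27 of 33 patients. On the Freedman basis the design has no slack, and a few sentences would settle the matter. The frailty model is also reserved for further covariate analysis, so it is not the stated main comparison.

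Parts of this stand. The unit is undefined, replacement is not mentioned, and unreplaced patients would cost power. But the rate behind the contrast is hypothetical. The at-least-one count, where unequal exposure would bite, is not among the planned analyses. Late choice is limited too: whether a tube or a patient leaves is decided at the chair, before wires are fitted and before that unit can have a recorded failure. Staff are stated to be masked and primer side is randomised, so there is no evident route by which the check would favour one primer. The wording also leans towards patients, since both headings that use the word sample concern patients; on that reading no three-tube patient arises.

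**Conclusion.** No change is needed. The wording is incomplete, but an analyst can fill it sensibly under either reading and still obtain a sound comparison. Patient exclusion costs roughly 1.2 to 1.3 power points for each of the first patients lost without replacement, on the Freedman basis; on the Schoenfeld basis power stays above 80% with 27 patients. Tube exclusion changes a denominator, with a crude shift of about a point or less in the example of five lower tubes.

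These sizes rest on assumed exclusion rates, four tubes per patient, independent tube failure where stated, and the plan's own approximation that ignores matching. The plan gives no within-patient correlation, so the power of the matched design itself cannot be computed. Naming the unit, stating whether excluded patients are replaced, and reporting exclusions by primer and arch would be tidy. But no planned result is shown to be biased or wrong without that.

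### No test is named as deciding for the primer comparison, and the arch, side, gender and age log-rank tests carry no exploratory label

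*Combined protocol and SAP*

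**What the plan says.** Aim and Objectives states one null hypothesis, of no difference in bond failure rate between Transbond MIP and Assure Plus. Objective 1 is the primer comparison. Objective 2 is "To compare the effectiveness of these primers between different arches, sides, gender and age differences".

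Sample Size refers to power "to show a statistically significant difference ($P < 0.05$) in proportions with at least one failed molar tube after 6 months". It reaches 33 per group with a log-rank test that ignores the matching. As an approximate allowance for matching it then takes 33 patients in total, to be analysed by a stratified log-rank test.

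Data Management and Analysis says: "To find if there is significant difference, the number of bonding failures will be compared using the chi-square test". It then compares "survival distributions with respect to primer material, tooth location (upper/lower, right/left side", gender and age by a log-rank test, with no mention of stratification, and adds a frailty Cox model for covariate effects. It gives no primary test, testing order, exploratory label or multiplicity rule, and no significance level of its own.

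**The concern.** Two things are left open. First, the primer hypothesis can be tested in three ways that differ in unit and in handling of the patient, and the stratified test named in Sample Size is missing from the analysis section. Which result decides the trial could be settled after the data are seen.

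Second, the four other factors sit beside the primer in one list of tests, and the only threshold in the document is P < 0.05. If it is applied to each, a chance arch, side, gender or age difference could be reported with the same weight as the primer result, although the trial was sized for the primer alone.

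**Working it through.** **1. Sample size reproduced.** Inputs from Sample Size: "This assumes a difference of 35 percentage points (45% versus 80%, hazard ratio = 3.6", 80% power, P < 0.05.
- Hazard ratio: ln(0.45)/ln(0.80) = 3.58. So 45% and 80% act as failure-free proportions, and the mean failure proportion is (0.55 + 0.20)/2 = 0.375.
- Freedman events, two-sided 0.05: (1.960 + 0.842)² × (4.6/2.6)² = 24.57.
- Per group: 24.57/0.375/2 = 32.8, that is 33, as stated. A one-sided 5% level gives 26 per group, so the stated number implies a two-sided 0.05 test of one contrast.

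**2. Five log-rank tests, no true effects, each holding 5% and independent.**
- Five tests: 1 − 0.95⁵ = 0.226.
- The four without primer: 1 − 0.95⁴ = 0.185.
- Upper bound for five under any dependence: 5 × 0.05 = 0.25, provided each test holds its level.

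**3. Whether each test holds its level.** Simulation with 33 patients, four tubes each, diagonal primer assignment, 6 months of follow-up and 3,000 trials per row. Assumptions not in the documents: 20% tube failure, gamma frailty shared within a mouth, and gender and age each as two groups of about half the patients (no age cut-point is given). Entries are the percentage of null trials with P < 0.05 by unadjusted tube-level log-rank.

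| Frailty variance | Primer | Arch | Side | Gender | Age | Any of five |
|---|---|---|---|---|---|---|
| 0 | 4.5 | 4.9 | 5.5 | 4.5 | 4.8 | 21.9 |
| 0.5 | 3.7 | 3.4 | 3.3 | 8.1 | 8.9 | 24.6 |
| 1 | 3.6 | 2.6 | 3.5 | 11.0 | 10.7 | 28.2 |
| 2 | 2.0 | 1.7 | 2.4 | 14.8 | 13.6 | 30.5 |

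A second set of runs gave 23% without clustering and 27 to 32% for variance 0.5 to 2, with gender and age rejecting in 8 to 17% of trials. At 37.5% tube failure the first set reached 39.8% for variance 2. The excess comes from gender and age: these are patient-level factors tested as if four tubes were four independent subjects. The within-mouth contrasts (primer, arch, side) become conservative.

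**4. Choice of primer test.** Setting: hazard ratio 3.6 and tube failure of 10.6% in the better arm, so that 1 − (1 − 0.106)² = 20% of primer sides have a failure when there is no frailty. The tube-level chi-square was set against the stratified log-rank on first failure per primer side. They disagreed at 0.05 in 15.0%, 17.8% and 19.8% of trials for frailty variance 0, 0.5 and 1 (400 trials each). Further runs gave 12 to 23%.

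**5. Unit of analysis.** At the same hazard ratio and across the assumed frailty values, the log-rank stratified by patient with the tube as unit had 81 to 89% power. First failure per primer side had 57 to 81%. Sample Size is worded "in proportions with at least one failed molar tube after 6 months", which is not the tube, so the unit has to be stated.

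**The case against.** The strongest reply is that a hierarchy already exists in substance. There is one null hypothesis, Objective 1 comes before Objective 2, and the sample size rests on one contrast, all pointing to the primer. The analysis section also has some order: chi-square to find a difference, log-rank next, Cox as further analysis. This stands as far as the factor is concerned. A reader might infer that all five comparisons are co-equal throughout the protocol; that is true of the one sentence, not of the document. What the reply does not settle is which primer test decides, or how covariate P values will be reported.

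A second reply is that no 5% rate across the set is promised, and that prognostic comparisons may not need family-wise control. This also stands. A reader might infer that the trial's error rate is 23% where 5% was claimed. The documents make no such claim, and adding covariate tests leaves the primer test's own level unchanged. Nor does any rule say that every P < 0.05 will be announced as a finding. The rates in the working apply only if the one stated threshold is used for each test.

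Third, the disagreement between primer tests was simulated where the null is false. It reflects differences in power and unit, and it should not be read as a false-positive rate. It shows that the verdict may depend on an unspecified choice.

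**Conclusion.** The point holds as one of specification. The primer is evidently the main question, but the analysis section does not carry over the stratified log-rank test from Sample Size and names no deciding test among three. It also leaves the arch, side, gender and age tests unlabelled.

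If P < 0.05 is applied to all five log-rank tests, the chance of at least one false significant result is about 23% under independence. With frailty variance 0.5 to 2 it is about 27 to 32% in one set of runs and 25 to 30% in the other (20% tube failure, age in two groups). Clustering, failure rate and age split are assumptions, so these figures show the order of size only. For the primer, the choice of test changes the verdict in about 12 to 23% of simulated trials at the design effect. This is ambiguity of verdict, not inflated type I error.

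There is also a mismatch of content. Objective 2, as worded, asks whether the primers' effectiveness differs by arch, side, gender and age; the planned log-rank tests compare survival between the levels of those factors.

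**What to change.** In Data Management and Analysis:

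1. Name Transbond MIP versus Assure Plus as the single confirmatory comparison, at two-sided 0.05, by a log-rank test stratified by patient, with the tube as unit and its first failure as the event. This keeps the stratified test of Sample Size. Say openly that the unit is the tube, whereas the sizing endpoint was at least one failed tube. The chi-square test and the Cox model are supportive and cannot overturn the result.
2. Label the arch, side, gender and age comparisons exploratory. Report hazard ratios with 95% confidence intervals from the already planned frailty Cox model, not from unadjusted tube-level log-rank tests. State how age enters the model. Where Objective 2 is meant as worded, add primer-by-factor interaction terms.
3. Do not rely on a Holm or Bonferroni correction of the unadjusted log-rank P values. It cannot control error when the gender and age tests do not hold their own level.

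The cost is a few sentences and a label on Objective 2, with no extra patients or data. The downside is that a covariate result with P < 0.05 can no longer be reported as an established effect.

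### The gender and age comparisons of tube survival use a log-rank test with no stated allowance for several tubes per patient, and the plan does not say that its patient-frailty option takes precedence

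*Combined protocol and SAP*

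**What the plan says.** All references are to the combined protocol and SAP.

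- **2- Randomization:** each patient receives both primers, each on one diagonal pair of quadrants. The section justifies the split mouth by the removal of differences between patients, such as chewing habits.
- **Sample Size:** the target is a difference "in proportions with at least one failed molar tube after 6 months", 45% versus 80%, hazard ratio 3.6, with 80% power. A log-rank ignoring the matching needs 33 per group. With matching, "an estimated 33 patients in total were required using a stratified log rank test for analysis".
- **5-Data collection:** "Only the first failure of tubes will be taken into consideration", so the recorded event belongs to the tube.
- **Data Management and Analysis:** "the number of bonding failures will be compared using the chi-square test". Kaplan–Meier curves for tubes are then compared by primer, arch, side, gender and age, the last part reading "gender and age will be then compared by means of a log-rank test". The section closes with "Further analysis to investigate the effects of covariates will be carried out using the frailty Cox regression model". It does not mention stratification, clustering, the frailty unit, or which result decides when two analyses of the same factor differ.

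**The concern.** An ordinary log-rank treats every tube as an independent observation. Tubes in one mouth share a patient, and the protocol's own case for the split-mouth design is that patients differ in ways that affect failure. Gender and age are constant within a patient, so all tubes in a mouth fall in the same group. Positive correlation then makes the variance used by the test too small, and it rejects too often.

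At stake is a secondary finding that tubes fail more often in one gender or age group, declared more often than the 5% level implies. The plan could also yield two p-values for gender, one from the log-rank and one from the frailty model, with no rule for choosing. For primer the issue is different: the power statement rests on a test and a unit that the analysis section does not name.

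**Working it through.** **1. Reproduce the plan's sample size.** Inputs from Sample Size: 45%, 80%, 80% power, P < 0.05 (taken as two-sided).
- Hazard ratio: ln(0.45)/ln(0.80) = 3.58, which matches 3.6 if 45% and 80% are proportions free of failure, i.e. 55% and 20% failing per primer side.
- Freedman events: 7.85 × (4.58/2.58)² ≈ 24.7.
- Mean proportion failing: (0.55 + 0.20)/2 = 0.375. Total 24.7/0.375 ≈ 66, or 33 per group. The stated figure reproduces.

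**2. Cluster size.** Inclusion requires intact first molars, and there are four quadrants. One tube per quadrant gives 4 tubes per patient and 33 × 4 = 132 tubes. This is inferred, not stated.

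**3. Error of the plain log-rank.** The documents give no within-mouth correlation ρ, so 0.1 to 0.3 is assumed, equal for all pairs of tubes. For gender the variance is about 1 + 3ρ times the assumed one; for primer, compared within the mouth, it is about 1 − ρ times. True error = 2 × (1 − Φ(1.96/√ratio)).

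| ρ | Gender ratio | Gender error | Primer ratio | Primer error |
|---|---|---|---|---|
| 0 | 1.00 | 5.0% | 1.00 | 5.0% |
| 0.1 | 1.30 | 8.6% | 0.90 | 3.9% |
| 0.2 | 1.60 | 12.1% | 0.80 | 2.8% |
| 0.3 | 1.90 | 15.5% | 0.70 | 1.9% |

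For gender this is 8.6/5 = 1.7 to 15.5/5 = 3.1 times nominal. The 132 tubes carry the information of 132/1.30 ≈ 102 independent tubes at ρ = 0.1 and 132/1.90 ≈ 69 at ρ = 0.3. With eight tubes per mouth instead of four (ratio 1 + 7ρ), the gender error would be about 13 to 27% over the same range.

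**4. Check by simulation.** Tube-level log-rank, 33 patients, 4 tubes each, no true effect.
- Correlation set directly, tube failure rates of 10.6, 22 and 37.5%, gender splits 16/17 and 10/23 (2,000 runs per setting): gender error 4.3–5.2% at ρ = 0, 7.4–9.1% at 0.1, 15.1–16.7% at 0.3.
- Gamma patient frailty with variance 0.5, 1 and 2 and 37.5% failing per side (tube correlation 0.10, 0.19, 0.34): gender about 8 to 9, 12 and 17%; primer about 4, 3 and 2%.
- The same frailty variances with an assumed 10% failing per side imply correlations of only 0.03, 0.05 and 0.10, and gender error is about 6 to 8%.

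**5. Can the stratified log-rank rescue gender and age?** No. Within a stratum defined by patient, all tubes have the same gender and age, so the stratum contributes nothing to that comparison.

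**6. Primer power at the plan's effect.** At zero correlation with the tube as unit: 89.8% for the plain log-rank and 88.5% for the patient-stratified one. With the primer side as unit and a stratified log-rank, power is about 78 to 80% at zero correlation. At frailty variance 0.5, 1 and 2 it is 85, 89 and 96% if 20% versus 55% failing is held fixed, but 74, 70 and 63% if the within-patient hazard ratio of 3.6 is held fixed.

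**The case against.** The strongest reply is that the null hypothesis concerns primer, and gender and age belong only to the second objective. The plan also goes on to a frailty Cox model for covariates, for which the patient is the natural unit, and Sample Size does name a stratified test. On this view only cross-referencing is missing. The correlation range is assumed, and the effect shrinks when failures are rare.

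Much of this stands. It limits the point to secondary analyses and makes its size conditional. It does not remove it: the log-rank is the test named specifically for gender and age, and the frailty model is described as further analysis, with neither unit nor precedence. Following the text as written gives a gender p-value with the wrong error rate whenever mouths are positively correlated.

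Three stronger readings are not supported:
- **That the primer result is anti-conservative.** Under equal correlation it is conservative. Inflation would need two same-primer tubes to be much more alike than tubes across primers, with a cross-primer correlation below half the same-primer one. Nothing in the documents suggests this, and same-primer tubes share neither arch nor side.
- **That the plan ignores clustering altogether.** The frailty model is there.
- **That the trial is underpowered.** With the tube as unit and a patient-stratified test, power at the plan's effect was above 80% in every scenario run.

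The second objective, "To compare the effectiveness of these primers between different arches, sides, gender and age differences", might also be read as requiring primer-by-factor interaction tests. That is one interpretation, and it calls for clarification; the documents do not establish an error there.

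**Conclusion.** The point holds for gender and age and should be fixed before analysis. The true error of the nominal 5% gender test is about 8.6 to 15.5% at within-mouth correlations of 0.1 to 0.3, and 5% if there is none. This rests on four tubes per mouth, roughly equal correlation between them, and a correlation that the documents do not give. Age is affected in the same direction; its size depends on a grouping that is not stated.

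For primer, the defect is a mismatch between sections: the 80% power refers to a stratified test of primer sides with any failure, while the analysis section names an unqualified log-rank on tubes. This casts no doubt on the type I error of the primer comparison under equal correlation.

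**What to change.** **Gender and age.** Replace the plain log-rank by the already planned frailty Cox model with the patient as the shared frailty, or by patient-clustered standard errors, and state that this result prevails. In simulation under no effect, the clustered log-rank gave 4.0–5.1% for gender and 3.6–4.0% for age in three groups. The frailty model gave 4.7–6.2% for gender, but reached 9.1% for three-group age at frailty variance 2, so clustering is the safer choice if age is grouped that way.

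**Primer.** Name in Data Management and Analysis one within-patient primary test consistent with Sample Size: the log-rank stratified by patient, or the patient-frailty Cox model with a primer term. Make the tube chi-square descriptive. If same-primer tubes might be more alike than cross-primer tubes, fix in advance a variance summed by patient for the stratified test. In one assumed scenario of that kind (correlations 0.27 and 0.08) the stratified tube test without it had 8.8% error, against 6.3% for the plain test and 4.4% with it.

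**Power.** Make the statement refer to the named test and unit. If the primer side is kept, show power under both assumptions in step 6, since they point in opposite directions once there is correlation.

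**Cost.** A few lines of wording and no new data. Gender and age will reach significance less often. With the tube as unit, the primer test loses about 1 point of power at zero correlation (89.8% to 88.5%; 86.8% with the patient-summed variance). Keeping the primer side costs more and may require revisiting the power claim or the number of patients.
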